	
For subjects terminating early for related and GI AEs, additional observational follow-up will occur monthly in clinic or by phone for up to 6 months or until the symptoms have resolved or stabilized, or the Investigator deems them to be irreversible, according to details described further in Section 6.5 of the protocol.
 
Beginning at signed informed consent and assent as age-appropriate, all AEs will be evaluated from the onset of the event until the time the event is resolved or medically stable, or until 30 days after the Exit or Early Discontinuation Visit, whichever comes first, with the exception of gastrointestinal (GI) AEs, detailed further below. Adverse events ongoing at the time that study treatment is discontinued may not be determined to be medically stable until 30 days after the Exit or Early Discontinuation Visit has been conducted, in which case additional visits after the Exit or Early Discontinuation Visit may be required. Subjects who discontinue dosing prematurely due to chronic/recurrent GI AEs will complete the Pediatric Eosinophilic Esophagitis Symptom Score (PEESS)TM version 2.0 questionnaire and return to the clinic for evaluation monthly for at least 6 months (if the subject is asymptomatic, telephone follow-up with an Investigator may substitute for in-clinic visit, at the Investigator's discretion). If chronic/ recurrent GI AEs persist beyond 6 months, subjects are to continue to be followed with monthly clinic visits (telephone follow-up with an Investigator may substitute for in-clinic visit, at the Investigator's discretion) until the symptoms have resolved or are assessed to have stabilized with optimal medical management or the Investigator deems them to be irreversible. The protocol provides additional specific guidance about symptomatic medical management and referrals to a gastroenterologist, as necessary, in Section 7.3.4.2 of the protocol.
 
A Data Safety Monitoring Committee has been established to monitor the study for safety.
 
Subjects who received AR101 and completed ARC007 will have the option to participate in the ARC011 study. The ARC011 study is an open-label safety extension study of ARC007 to evaluate the safety and tolerability of 300 mg/d maintenance dosing for up to 6 months. After completing Study ARC011, subjects will be able to proceed to ARC008 for further maintenance dosing.
 
Subjects who received active treatment but did not reach 300 mg/d within 40 weeks or were unable to tolerate 300 mg daily for 2 weeks by 48 weeks after Day 1 will not be eligible for enrollment in ARC011 or ARC008.
 
Subjects who received placebo and completed ARC007 will be offered up-dosing and maintenance treatment with AR101 in the ARC008 study. In ARC008, these subjects will undergo an escalation schedule identical to that for active subjects in the ARC007 study and then continue on maintenance dosing at 300 mg/d.
 
All subjects who enter ARC008 will be allowed to continue receiving AR101 until it becomes commercially available or the development program is terminated.

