Study Duration	Screening/baseline for up to 21 days. Dosing typically for 22 to 48 weeks, unless double-blind treatment is extended for subjects waiting for activation of follow-on protocols. Up to 6 months (or more) additional observational follow-up for subjects terminating early for GI AEs.

Protocol ARC007 Amendment 2.0 Synopsis	
Title	REAL-WORLD AR101 MARKET-SUPPORTING EXPERIENCE STUDY IN PEANUT-ALLERGIC CHILDREN AGES 4 TO 17 YEARS
Primary Endpoint	The primary endpoint of this study is the frequency of treatment-emergent AEs, including serious AEs, during the overall study period.
Secondary Endpoints	
Secondary Endpoints
 
 Frequency of premature discontinuation of dosing due to AEs Frequency of premature discontinuation of dosing due to chronic/recurrent GI AEs Proportion of chronic / recurrent GI AEs resolving at 2, 4, and \geq 12 weeks following cessation of dosing Frequency of allergic reaction (hypersensitivity) AEs occurring during up-dosing, normalized for duration of treatment Frequency of anaphylaxis as defined in the protocol Frequency of use of epinephrine as a rescue medication Frequency of accidental ingestions of peanut and other allergenic foods and severity of any resultant reactions Assessment of asthma control using the Asthma Control Test (ACT) questionnaire and frequency of use of asthma rescue medication (short acting beta-agonists) in subjects with asthma
Exploratory Endpoints	
Exploratory Endpoints
 
 Changes in peanut-specific and peanut component-specific serum immunoglobulin E (IgE) and immunoglobulin G subclass 4 (IgG₄) levels Changes in peanut skin prick test (SPT) mean wheal diameter Changes in Total Nasal Symptom Score in subjects with allergic rhinitis Changes in scores of the food allergy related quality of life questionnaire (FAQLQ) and food allergy independent measure (FAIM) questionnaire

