The primary endpoint of the study is the frequency of TEAEs, including SAEs, during the overall study period. Secondary endpoints are frequency of premature discontinuation of dosing due to AEs; frequency of premature discontinuation of dosing due to chronic / recurrent GI AEs; proportion of chronic / recurrent GI AEs resolving at 2, 4, and \geq 12 weeks following cessation of dosing; frequency of allergic reaction (hypersensitivity) AEs occurring during up-dosing, normalized for duration of treatment; frequency of anaphylaxis as defined in the protocol; frequency of use of epinephrine as a rescue medication; frequency of accidental ingestions of peanut and other allergenic foods and severity of any resultant reactions; and assessment of asthma control using the Asthma Control Test (ACT) questionnaire and frequency of use of asthma rescue medication (short acting beta-agonists) in subjects with asthma.

Exploratory endpoints include changes in peanut- and peanut component-specific serum IgE and IgG₄ levels, changes in peanut SPT wheal diameter, changes in Total Nasal Symptom Score in subjects with allergic rhinitis, and changes in scores of the food allergy related quality of life questionnaire (FAQLQ) and food allergy independent measure (FAIM) questionnaire.

The Screening/Baseline Period is up to 21 days. Eligible subjects will be randomized in a 2:1 ratio to receive escalating doses of either AR101 or placebo, in 2 phases. Randomization will be stratified by age group (4 to 11 years and 12 to 17 years). Following a 2-day initial escalation phase, the up-dosing phase will be a minimum of 20 to a maximum of 40 weeks in duration in order to achieve the 300 mg/d dose level. Subjects reaching this dose of 300 mg/d will continue for an additional 2 weeks to ensure tolerability of the 300 mg/d dose. If the subject is unable to tolerate the 300 mg dose for the 2-week period, dosing may continue up to a maximum of 48 weeks after Day 1 to ensure tolerability prior to exiting the study. For subjects terminating early for GI AEs, additional observational follow-up will occur monthly in clinic or by phone for up to 6 months or until the symptoms have resolved or stabilized, or the Investigator deems them to be irreversible, according to details described further in Section 6.5.

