Beginning at signed informed consent and assent as age-appropriate, all AEs will be evaluated from the onset of the event until the time the event is resolved or medically stable, or until 30 days after the Exit or Early Discontinuation Visit, whichever comes first, with the exception of GI AEs, detailed further below. Adverse events ongoing at the time that study treatment is discontinued may not be determined to be medically stable until 30 days after the Exit or Early Discontinuation Visit has been conducted, in which case additional visits after the Exit or Early Discontinuation Visit may be required. Subjects who discontinue dosing prematurely due to chronic/recurrent GI AEs will complete the Pediatric Eosinophilic Esophagitis Symptom Score (PEESS™ version 2.0) questionnaire and return to the clinic for evaluation monthly for at least 6 months (if the subject is asymptomatic, telephone follow-up with an Investigator may substitute for in-clinic visit, at the Investigator's discretion). If chronic/recurrent GI AEs persist beyond 6 months, subjects are to continue to be followed with monthly clinic visits (telephone follow-up with an Investigator may substitute for in-clinic visit, at the Investigator's discretion) until the symptoms have resolved or are assessed to have stabilized with optimal medical management or the Investigator deems them to be irreversible. The protocol provides additional specific guidance about symptomatic medical management and referrals to a gastroenterologist, as necessary, in Section 7.3.4.2. Treatment will be administered in a double-blind fashion.

A DSMC has been established to monitor the study for safety.

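### The protocol states follow-up after stopping for GI adverse events in two conflicting ways, and the SAP's resolution summary has no place for a case that leaves follow-up unresolved

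*Protocol*

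**What the plan says.** The protocol describes this follow-up in a short form and a detailed form.

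**Short form.** Section 3 (Study Design) says that "additional observational follow-up will occur monthly in clinic or by phone for up to 6 months or until the symptoms have resolved or stabilized", or until the investigator judges them irreversible, "according to details described further in Section 6.5". The Study Design row of the synopsis has the same sentence for a wider group: "For subjects terminating early for related and GI AEs, additional observational follow-up will occur monthly in clinic or by phone for up to 6 months". It also points to Section 6.5.

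**Detailed form.** The next paragraph of Section 3 has children who stop for chronic/recurrent GI events "return to the clinic for evaluation monthly for at least 6 months (if the subject is asymptomatic, telephone follow-up with an Investigator may substitute"; the parenthesis goes on to leave that substitution to the investigator. It continues: "If chronic/recurrent GI AEs persist beyond 6 months, subjects are to continue to be followed with monthly clinic visits", now with phone contact at the investigator's discretion. The synopsis repeats this form in the same row as the short form, again with "return to the clinic for evaluation monthly for at least 6 months". Section 7.3.4.2 and footnote b of Appendix 1 also carry it, with small differences shown below.

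The Study Duration row of the synopsis has a third wording: "Up to 6 months (or more) additional observational follow-up for subjects terminating early for GI AEs".

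**Analysis.** The timing of resolution after stopping is a secondary endpoint (Protocol 9.2.2). SAP 4.2 and 9.8.2 take discontinuers whose GI events were ongoing and sort them into four classes: resolved before 2 weeks, at 2 to 4, at 4 to 12, and at 12 weeks or later. SAP 7.2 bases categorical percentages on nonmissing data unless stated otherwise. SAP 7.2.1 does not impute a completely missing stop date.

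**The concern.** A child who stops for chronic/recurrent GI events falls under both forms, and the text gives neither precedence. One form can be read as an upper limit on follow-up and the other sets a lower limit. One allows phone contact without condition and the other ties it to absence of symptoms. The pointer to Section 6.5 does not help: that section covers assessment of allergic reactions, their treatment and dose adjustment, and gives no schedule after discontinuation.

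Two things are at stake. Sites may follow the same kind of case for different lengths of time, although other procedures assume the longer period. Examples are the 12-week check on symptomatic therapy in Section 7.3.4.2 and the sub-study's final saliva sample at the sixth monthly visit (Appendix 7). Also, a case closed while stable but unresolved has no resolution date, and SAP 9.8.2 provides classes only for events that resolved.

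**Working it through.** **Step 1: the statements side by side.**

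| Place | Who | Length | Phone | Ends when |
|---|---|---|---|---|
| Synopsis, Study Design, short | Stop for related and GI events | Up to 6 months, or until an end condition | No condition | Resolved, stabilised or irreversible |
| Section 3, short | Stop for GI events | As above | No condition | As above |
| Synopsis, Study Duration | Stop for GI events | Up to 6 months, possibly more | Not stated | Not stated |
| Synopsis and Section 3, detailed | Stop for chronic/recurrent GI events | 6 months minimum, then open-ended if persisting | First 6 months: only if asymptomatic. Later: at discretion | Resolved, stabilised or irreversible |
| Section 7.3.4.2 | As above | As above | As above | Resolved or stabilised; irreversible not listed |
| Appendix 1, footnote b | As above | As above | First 6 months: only if asymptomatic. Later: no phone option given | Resolved or stabilised; irreversible not listed |

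The conflicts concern length, phone rule, population and end rule.

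**Step 2: does a 6-month limit hide the endpoint's cut-points?** Six months is 6 × 365.25 / 12 = 182.6 days, and 182.6 / 7 = 26.1 weeks after the last dose. Counted from the Early Discontinuation Visit at day 14 (Section 6.8), it is (182.6 + 14) / 7 = 28.1 weeks. The last cut-point is week 12, so 6 months passes it by 26.1 − 12 = 14.1 weeks. A 6-month limit alone would lose only resolutions after about week 26, all in the open last class.

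**Step 3: how early could a stabilised case be closed?** Sections 3, 4.3.2 and 7.6 bar a judgement that an ongoing event is stable until 30 days after the Early Discontinuation Visit. That visit is at day 14, with a window of −3 to +7 days (Section 6.8).

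- Nominal: 14 + 30 = 44 days, and 44 / 7 = 6.3 weeks.
- Earliest: 11 + 30 = 41 days, and 41 / 7 = 5.9 weeks.
- Latest: 21 + 30 = 51 days, and 51 / 7 = 7.3 weeks.

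By then the first two classes (before 2 weeks, 2 to 4 weeks) are already settled. The classes that can lose a subject are 4 to 12 weeks and 12 weeks or later. Under the detailed form, the same child would be followed for at least 6 months.

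**Step 4: what the SAP does with such a child.** No stop date means no class in 9.8.2. If the nonmissing-data rule of SAP 7.2 is applied, the child also leaves the denominator, and the percentage in every class rises. SAP 7.2 has a second rule, subjects at risk, for incidence data such as adverse events. Section 9.8.2 does not say which of the two governs this summary.

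**Step 5: can the effect be sized?** The nearest figure is ARC001, where 4 of 29 AR101 subjects discontinued because of GI events (Protocol 1.2.1 and Appendix 7). Two thirds of the maximum 500 is 333, and 333 × 4/29 = 46. The exact 95% interval for 4/29 is 3.9% to 31.7%, or about 13 to 105 of 333. That counts discontinuers, whereas SAP 9.8.2 counts only those with ongoing events. Neither document gives a rate of closure while unresolved.

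**The case against.** The strongest reply is that the detailed rule agrees on length wherever it appears: the synopsis, Section 3, Section 7.3.4.2 and footnote b. Sections 4.3.2 and 7.6 send sites to Section 7.3.4.2. The short sentence is a design summary that defers to details elsewhere. It does not say which of its limits comes first, and the Study Duration row allows for more than 6 months. The groups are worded differently, so a general rule with a specific rule beneath it is possible.

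Much of this stands, and it rules out three stronger readings that a reader might infer.

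- *That follow-up is capped at 6 months and so late resolution is hidden.* A cap is only one reading, and every cut-point lies well inside 26 weeks.
- *That a site could close a case in the first month as stable.* The 30-day rule puts the earliest such judgement at about week 6.
- *That relapse or an eosinophilic esophagitis workup would go unseen.* Section 4.3.2 asks everyone who stops wholly or partly for GI events to complete the PEESS questionnaire monthly and keep the diary for 6 months, whether or not symptoms persist. Section 7.3.4.2 calls for gastroenterology referral if symptoms have not fully resolved within 6 weeks, and for sites to obtain the specialist's records.

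The SAP listing also gives weeks to resolution for ongoing events, so an unresolved subject can be found by hand.

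The reply does not remove the conflict. No passage states a general-plus-specific hierarchy, the synopsis places both forms in one row, and the pointer to Section 6.5 leads nowhere useful. Nor does a listing settle the denominator of the summary table.

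**Conclusion.** The point holds as a minor error: the protocol is wrong as written on length, phone contact, population and end rule, and the Section 6.5 cross-reference is misdirected. The consequence is limited. Only a site that acts on the short statement could close a stabilised, unresolved case before 6 months, from about week 6, and only the two later resolution classes can lose that subject.

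This assumes that the 30-day rule applies to GI events. Section 4.3.2 states it without a GI exemption. It also assumes that a judgement of irreversibility would come no sooner; the documents set no separate floor for it.

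No numerical effect follows from the documents. A reader might be tempted to take about 46 discontinuers, assume that 10% to 20% are closed early, and report a 10- to 20-point shift in the resolved proportion. That only restates the assumed closure share. It also requires every closed case to have resolved later, and it uses a denominator wider than the SAP's.

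The SAP gap is independent of which follow-up rule is chosen. Subjects whose follow-up ends unresolved have no row and could drop out of the denominator of a secondary endpoint.

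**What to change.** **Protocol.** Reconcile both statements in the synopsis Study Design row, the Study Duration row, both paragraphs of Section 3, Section 7.3.4.2 and Appendix 1 footnote b. They should give one duration, one phone rule (including after 6 months), one end rule (including whether irreversibility ends follow-up) and one population. Which rule applies is for the sponsor's clinical team. Redirect the Section 6.5 cross-reference in the synopsis and Section 3 to Section 7.3.4.2.

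**SAP 9.8.2.** State that the denominator is all discontinuers with ongoing chronic/recurrent GI events. Add a category for those unresolved at the end of follow-up, and summarise their follow-up time.

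**Cost.** A protocol clarification and one table row. The reported resolved proportion may be lower than it would be with unresolved subjects left out.

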3.1 Study Periods

The study consists of a screening period after which eligible subjects will proceed through 2 study periods, as tolerated:

- Initial Escalation
- Up-Dosing

3.2 Initial Escalation

All Initial Escalation doses will be administered by investigational site personnel to the subjects under direct supervision. Eligible subjects will be randomized and receive treatment with IP on Day 1, starting at a dose of 0.5 mg, increasing the dose at 20- to 30-minute intervals to a maximum dose of 6 mg ([Table 1](#)), according to the Schedule of Events (SOE) in [Appendix 1](#). Subjects who fail to tolerate ≥ 3 mg dose on Day 1 will be considered escalation failures and will be discontinued. Subjects who tolerate ≥ 3 mg dose on Day 1 will undergo confirmatory dosing of a single 3 mg dose on the following day, Day 2. Subjects who do not tolerate this confirmatory dose will be discontinued. Subjects who tolerate this confirmatory dose will enter the Up-Dosing Period.

Table 1: Initial Escalation Schedule

Initial Escalation Schedule		
Day 1 Dose Number	Investigational Product Dose, mg ^a	Cumulative Dose, mg
1	0.5	0.5
2	1	1.5
3	1.5	3
4	3	6
5	6	12
Day 2 Dose Number	Investigational Product Dose, mg	Cumulative Dose, mg
1	3	3

^a All mg doses shown refer to milligrams of peanut protein or the equivalent placebo dose.

Doses will be delivered at 20 to 30 minute intervals under direct observation.

Capsules are to be opened, contents sprinkled over an age-appropriate food, and mixed thoroughly and consumed.

Day 1: Subjects who are unable to tolerate at least a single dose of 3 mg at the end of Day 1 will be considered escalation failures. Subjects who tolerate ≥ 3 mg on Day 1 will return on Day 2 to receive a 3 mg single dose.

Day 2: Subjects with either no symptoms or mild symptoms on Day 2 at 3 mg will start daily home-dosing at 3 mg on Day 3.

Subjects with moderate or severe symptoms at 3 mg on either Day 1 or Day 2 will be considered escalation failures and will be discontinued from the study.

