Treatment Description	
Screening/Baseline: All subjects will undergo the screening procedure outlined in Section 6.2 of the protocol and eligible subjects will be randomized 2:1 to active treatment with AR101 or placebo.
 
Initial Escalation (2 days): Eligible subjects will be randomized and initiate CODIT starting at a dose of 0.5 mg of IP, and then increase the dose incrementally at 20- to 30-minute intervals over the course of a single day to a maximum dose of 6 mg. Subjects who fail to tolerate \geq 3 mg dose on Day 1 will be considered escalation failures and will be discontinued. Subjects who tolerate \geq 3 mg dose on Day 1 will undergo confirmatory dosing of a single 3 mg dose on the following day, Day 2. Subjects who tolerate this confirmatory dose will enter the Up-Dosing Period. Subjects who do not tolerate this confirmatory dose will be discontinued. Initial escalation failures, either on Day 1 or Day 2, will be asked to return to the clinical research center (CRC) 14 days following the last dose of IP to undergo an Early Discontinuation Visit.
 
Up-dosing: Subjects will receive IP starting at a dose of 3 mg once daily and will gradually escalate every 2 weeks to a maximum of 300 mg once daily, according to the Up-Dosing Schedule (see Table 2 of the protocol). Subjects who are unable to escalate to 300 mg within 40 weeks or who are unable to tolerate 300 mg daily for 2 weeks by 48 weeks after Day 1 will be considered escalation failures.
 
Subjects able to escalate to 300 mg/d will continue taking the 300 mg dose for an additional 2 weeks and then exit the study, providing all exit requirements are met. If the subject is unable to tolerate the 300 mg dose for the 2-week period, dosing may continue up to a maximum of 48 total weeks since Day 1 to ensure tolerability prior to exiting the study.
 
Unblinding of each subject’s treatment assignment will occur at study completion per the conditions stated previously, and the subjects will have the option to enter a rollover study depending on their ARC007 treatment

Protocol ARC007 Amendment 2.0 Synopsis	
Title	REAL-WORLD AR101 MARKET-SUPPORTING EXPERIENCE STUDY IN PEANUT-ALLERGIC CHILDREN AGES 4 TO 17 YEARS

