If Day 2 dosing is completed with no symptoms detected after 1.5 hours of post-dose observation, the subject will be able to leave the CRC. If the subject exhibited mild symptoms, the duration of the observation period should be a minimum of 1 hour after resolution of the symptoms. For moderate symptoms, the observation period should be extended to a minimum of 2 hours after resolution of the symptoms. For severe symptoms, the subject should be observed for a minimum of 3 hours after resolution of the symptoms, either at the CRC or an emergency facility, as appropriate.

Any subject deemed to have severe symptoms that include hypoxia, hypotension, or change in mental status (stage 3 anaphylaxis defined in [Appendix 4](#)), or who receives intensive therapy (to be determined by the Investigator, but may include such interventions as IV epinephrine, intubation, or admission to an intensive care unit) for an allergic reaction at any time should be discussed with the Medical Monitor and discontinued from the study.

If dose-limiting symptoms occur on Day 2, there will be no further dosing, and the subject will be classified as an escalation failure and a non-responder for the purpose of statistical analyses. The subject will be asked to return to the CRC 14 days following the last dose of IP to undergo an Early Discontinuation Visit (Section [6.3.6](#)). AEs will be evaluated from the onset until the event is resolved or medically stable, or until 30 days after the Early Discontinuation Visit, whichever comes first.

Those subjects who tolerate the single 3 mg dose of IP on Day 2 will be dispensed a 2-week supply of IP at the 3 mg/d dose level. They will be instructed to continue daily oral dosing at home, starting the following day (Study Day 3), and to continue daily home-dosing at that dose level for 2 weeks until next escalation.

On Day 3, the site is required to make telephone contact with the subject's parent/guardian to enquire if any AEs (including allergic symptoms) occurred subsequent to the subject leaving the clinic, and to provide assistance in recording of, and responding to, any such events.

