6.5.2 Assessment of the Tolerability of an Individual Dose of Investigational Product

Determination of the tolerability of any individual dose of IP should be based on an assessment of acute symptoms occurring in close temporal succession to dosing.

In general, the severity of allergic symptoms elicited at a particular dose of IP will define the tolerability of that dose of IP. The place where there is the greatest need for clinical judgment in determining the tolerability of a dose is when the dose elicits mild allergic symptoms. [Table 3](#) illustrates the likely combinations of symptom severity and tolerability:

Table 3: Allergy Symptom Severity and Investigational Product Dose Tolerability

Symptom Severity	Assessed Tolerability
None	Tolerated
Mild, oropharyngeal symptoms only	Tolerated
Mild, meeting pre-defined tolerability criteria (Section 6.5.1)	Tolerated
Mild, not meeting pre-defined tolerability criteria (Section 6.5.1)	Not tolerated
Moderate (except for rare exceptions, Section 6.5.1)	Not tolerated
Severe	Not tolerated

In general, the severity of an allergic reaction will correspond to the maximum severity of any of its symptoms.

No symptoms: If a dose elicits no symptoms, the dose will be assessed as tolerated.

Mild symptoms: When dosing with IP elicits an acute reaction characterized by the appearance of only a mild symptom or symptoms, the Investigator will be required to assess whether the

dose was or was not tolerated. The determination of tolerability must be made on the basis of clinical judgment. The following are presented as guidelines for determining whether a dose associated with the emergence of a mild symptom or symptoms was tolerated. A dose eliciting only mild symptoms may be considered to be tolerated if the symptoms are:

- Isolated to a single organ system
- Resolve with no pharmaceutical intervention or with a single oral administration of an H1 antihistamine
- Do not require administration of epinephrine
- Are not worsening in intensity or distribution over time
- Resolve, or shows definite signs of resolving, in under 1 hour
- Do not include objective wheezing

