Based on experience from Phase 2 study results, most acute allergic responses to dosing that are characterized by mild symptoms would be anticipated to meet the above criteria. If, however, an allergic response to dosing is characterized by mild symptoms that do not meet all of the above criteria (eg, has mild symptoms occurring in 2 or more organ systems, requires treatment with 2 doses of antihistamine or 1 dose epinephrine, shows progression in severity or distribution over time, is protracted in duration, or includes objective wheezing), then even though the allergic symptoms may be mild, the dose should be assessed to be not tolerated. If a dose elicits mild symptoms that do not fit all of the above criteria and the dose is assessed to be tolerated, then a brief explanation as to why the dose was considered tolerated must be recorded in the CRF.

Moderate symptoms: In general, if a dose elicits moderate symptoms, the dose will be assessed as not tolerated. There may, however, be rare occasions when a dose eliciting moderate symptoms could be assessed as tolerated. Generally, this would only be the case for a transient, self-limited (requiring no intervention and resolving completely) symptom occurring in a single organ system. In addition, typically the symptom would be subjective only. Any dose associated with moderate symptoms and assessed as tolerated must be accompanied by a brief explanation in the CRF as to why the dose was considered tolerated.

Severe symptoms: If a dose elicits severe symptoms, the dose will be assessed as not tolerated. Whenever a dose elicits an allergic response characterized by 1 or more severe symptoms, the crucial decision, after adequate treatment for the allergic reaction has been administered, will be to determine whether the subject should continue in the study, dosing at a reduced dose level, or be discontinued early from the study.

The determination of tolerability will decide the course of action to be taken in response to dose-related reactions (Section 6.5.3).

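### The Day 2 note under Table 1 releases every child with mild symptoms to home dosing, although the rest of the protocol requires the confirmatory 3 mg dose to have been tolerated

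*Protocol*

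**What the plan says.** Two notes under Table 1 in Protocol 3.2 deal with the outcome of the Day 2 dose. The first is the release rule: "Subjects with either no symptoms or mild symptoms on Day 2 at 3 mg will start daily home-dosing at 3 mg on Day 3". The second is the failure line: "Subjects with moderate or severe symptoms at 3 mg on either Day 1 or Day 2 will be considered escalation failures". Neither mentions a mild reaction that was not tolerated.

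Three other places make tolerability the condition:

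- The body text of 3.2, above the table: "Subjects who do not tolerate this confirmatory dose will be discontinued".
- The synopsis, under Treatment Description: "Subjects who tolerate this confirmatory dose will enter the Up-Dosing Period. Subjects who do not tolerate this confirmatory dose will be discontinued".
- Section 6.3.2, which governs the Day 2 visit and the dispensing of product: "If dose-limiting symptoms occur on Day 2, there will be no further dosing, and the subject will be classified as an escalation failure", and "Those subjects who tolerate the single 3 mg dose of IP on Day 2 will be dispensed a 2-week supply".

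Section 6.5.2 says how tolerability is decided when symptoms are mild: "The determination of tolerability must be made on the basis of clinical judgment". It lists criteria that a mild reaction should meet to count as tolerated. Its examples of reactions that miss them include one that "requires treatment with 2 doses of antihistamine or 1 dose epinephrine". Table 3 has a separate row for mild reactions outside the criteria and labels it not tolerated.

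**The concern.** Mild and tolerated are different categories in this protocol, and the Day 2 note treats them as one. Site staff may well use a note under a dosing table as a quick reference, and this one gives a complete instruction. Nothing in the protocol says which text prevails if the note and the body disagree.

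Day 2 is the last supervised dose before home dosing starts. Sections 3.3 and 6.5.5 forbid dosing below 3 mg a day, so no lower step is available here. A child on AR101 who was released in error would repeat at home the same dose that had just been judged not tolerated. The Day 3 telephone call (6.3.2) and the return to clinic after a suspect home dose (6.5.3.1) reduce the risk, but both come after product has been handed over.

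**Working it through.** The plan gives no figure on this point, so the check compares what each text does with each possible Day 2 outcome.

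| Day 2 outcome at 3 mg | Notes under Table 1 | 3.2 body text, synopsis, 6.3.2 |
|---|---|---|
| No symptoms | Home dosing | Home dosing |
| Mild, assessed as tolerated | Home dosing | Home dosing |
| Mild, assessed as not tolerated | **Home dosing** | **Discontinued** |
| Moderate or severe | Escalation failure | Escalation failure (6.5.4 decides a moderate reaction at this dose on severity alone) |

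The texts disagree in one row only. That row can occur, because 6.5.2 describes its contents: more than one organ system involved, a second antihistamine dose, a dose of epinephrine, progression, long duration or objective wheeze. It stays empty for any child whose investigator judges the dose tolerated despite missing a criterion and records why in the CRF, as 6.5.2 allows.

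Section 6.5.5.1 already uses suitable wording for another situation. After a severe reaction, a child counts as tolerating the reduced dose if there are no symptoms, or mild ones judged tolerated. The Day 2 note lacks that condition.

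For the number of extra home doses, the tolerability rule gives 0. Under the note:

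- Table 2, footnote a, counts Day 2 within the two-week interval. Home doses fall on Days 3 to 15: 15 − 3 + 1 = 13 doses, and 13 × 3 mg = 39 mg.
- Counting two weeks from Day 3, as 6.3.2 does: 14 doses, and 14 × 3 mg = 42 mg.
- With the visit window of 2 days either way (6.8): 13 − 2 = 11 doses (33 mg) to 14 + 2 = 16 doses (48 mg).
- If the Day 3 home dose is suspected of not being tolerated and the next is given in clinic (6.5.3.1): 1 dose, 3 mg.

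None of these is an upper limit. Section 6.3.3 lets the investigator postpone escalation by 1 to 2 weeks when a dose level is not well enough tolerated. On the nominal schedule that gives 13 + 7 = 20 to 14 + 14 = 28 doses (60 to 84 mg). Kits hold 21 daily doses (5.1), and a child for whom nothing intervenes would go on to 6 mg. A child on placebo receives no peanut protein from any of these doses.

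**The case against.** The strongest reply is that the protocol already has the rule right. It stands in the paragraph above the table, in the synopsis, and in 6.3.2, the section that controls dispensing. For the error to occur, an investigator would have to judge a dose not tolerated and then dispense against all three because of a table note. This stands as a reason to expect few cases. It does not reconcile the texts, since the note is itself an instruction and cannot be followed together with the others for these children.

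The failure line can also be defended. It agrees with 6.5.4, where a moderate reaction at 3 mg or below ends escalation on severity alone, and it does not say that nothing else counts as failure. That is fair. The line is incomplete rather than wrong, and the error lies in the release note.

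A reader might infer three stronger points that the documents do not support:

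- That a mild reaction treated with epinephrine is a second, separate conflict. Under 6.5.2 one epinephrine dose already puts a mild reaction in the not-tolerated group, so this case largely sits inside the first. What remains is a dose called tolerated despite epinephrine. The epinephrine sentence in 6.5.4 makes this a cause to end the initial escalation. It does not itself bar all further product, and on Day 2 the only dose has already been given.
- That 6.5.4 requires every child who needs a second medication or a second antihistamine dose to stop on Day 2, even if the dose is called tolerated. That rule opens with a general qualifier, and parts of the section are written for the multi-dose Day 1. Section 6.3.1 brings back for Day 2 a child whose dose-limiting symptoms occurred only at 6 mg.
- That 42 or 48 mg is the most a misdirected child could receive. As shown in the working, it is not.

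**Conclusion.** The conflict is real and narrow. The Day 2 note is wrong for one group: children with a mild reaction that the investigator assesses as not tolerated. For every other outcome the texts agree.

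The group is probably small. Section 6.5.2 expects most mild reactions to meet the criteria, and 6.5.4 regards epinephrine for mild symptoms as unlikely. Neither gives a rate, so no count can be offered. The extra exposure per affected child can be as little as one dose and has no reliable cap.

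The statistical effect is limited. Every dosed child stays in the safety population (SAP 6.1). Only the counts of children entering each study period and of those discontinued (SAP 9.1), and any tally of escalation failures, could shift. A reader might infer that the safety comparison is compromised or that the design has no tolerability gate. The documents support neither.

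The conclusion rests on reading the note literally and on taking dose-limiting in 6.3.2 as equivalent to not tolerated. Without that second assumption the conflict still stands on 3.2, the synopsis and the dispensing sentence in 6.3.2.

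**What to change.** Make two edits under Table 1.

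- In the Day 2 note, keep the reference to children with no symptoms and replace the bare reference to mild symptoms with: *mild symptoms only, assessed as tolerated under Section 6.5.2*.
- In the failure line, after the reference to moderate or severe symptoms on Day 1 or Day 2, add: *or with mild symptoms on Day 2 that are assessed as not tolerated*.

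The edits should not create a mandatory Day 2 stop tied to stopping criteria in 6.5.4. The protocol defines no such term, part of that rule is qualified, and the result would be a new clinical rule rather than a reconciliation of existing text.

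The cost is small. Section 10.1 requires sponsor and IRB/EC approval and submission to health authorities before an amendment is implemented, so the edits are best carried in the next one. Data collection and analysis do not change.
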